16. SAFETY ASSESSMENTS AND MONITORING

16.1. Definition of an Adverse Event

An AE is any untoward medical occurrence associated with the use of a drug in humans, whether or not considered drug related. An AE can therefore be any unfavorable and unintended sign (including an abnormal laboratory finding), symptom or disease temporally associated with the use of a study drug/study intervention, whether or not related to the study drug/study intervention.

Any laboratory abnormality that is deemed to be clinically significant in the opinion of the investigator will be considered an AE and should be recorded in the eCRF, whether or not it is related to the study drug.

Stable chronic conditions that are present prior to clinical trial enrollment and do not worsen are not considered AEs and will be accounted for in the subject's medical history.

The following can be considered AEs:

- An exacerbation of a pre-existing illness
- An increase in frequency or intensity of a pre-existing episodic event or condition
- A condition detected or diagnosed after the initiation of treatment with study medication, even though it may have been present prior to the start of the study
- Continuous persistent disease or symptoms present at baseline that worsen after signing the informed consent or following the initiation of treatment with study medication

The following are **not** considered AEs:

- Medical or surgical procedures (e.g., surgery, endoscopy, tooth extraction or transfusion); the condition that leads to the procedure is an AE
- Pre-existing disease or conditions present or detected at the start of the study that do not worsen
- Situations where an untoward medical occurrence has not occurred (e.g., hospitalizations for cosmetic surgery or elective surgery or social/convenience admissions)
- The disease being studied, or signs or symptoms associated with the disease, unless more severe than expected for the subject's condition or a worsening of the disease being studied

16.2. Definition of a Serious Adverse Event

A SAE is defined as an AE meeting one of the following outcomes:

- Death
- Life-threatening event
- Inpatient hospitalization or prolongation of existing hospitalization

- Persistent or significant disability/incapacity or substantial disruption of the ability to conduct normal life functions
- Congenital anomaly or birth defect

Any other important medical event that may not result in one of the above outcomes may be considered a SAE when, based upon appropriate medical judgment, the event may jeopardize the participant and may require medical or surgical intervention to prevent one of the outcomes listed above.

A life-threatening AE is any AE that places the subject, in the view of the investigator, at immediate risk of death from the AE as it occurred. It does not include an AE that, had it occurred in a more severe form, might have caused death.

16.3. Events of Clinical Interest

Not Applicable

16.4. Overdose

This refers to the administration of a quantity of a medicinal product given per administration or cumulatively, which is above the maximum recommended dose according to the authorized product information.

An overdose can occur if a subject has taken, accidentally or intentionally, a drug administered in a dose exceeding the protocol-specified dose. An overdose must be reported within 24 hours of the site becoming aware of the overdose if such overdose occurs with an associated SAE. If an overdose occurs without an associated SAE, the overdose must be reported within 5 working days and documented in the subject's medical record as well as in the dosing section of the eCRF.

16.5. Pregnancy

Female subjects who become pregnant should be immediately discontinued from the study and followed up to determine the outcome of the pregnancy. The pregnancy must be reported to the Sponsor within 24 hours of the site becoming aware of the pregnancy. If the pregnancy ends for any reason before the anticipated date, the investigator should notify the Sponsor. At the completion of the pregnancy, the investigator will document the outcome of the pregnancy. If the outcome of the pregnancy meets the criteria for immediate classification as an SAE (i.e., postpartum complication, spontaneous abortion, stillbirth, neonatal death or congenital anomaly), the investigator should follow the procedures for reporting an SAE.

16.6. Unexpected Adverse Event

An AE is considered "unexpected" if it is not listed in the IB or is of greater specificity or severity than those that have been observed with the particular study drug being tested. For example, under this definition, hepatic necrosis would be unexpected (by virtue of greater severity) if the IB referred only to elevated hepatic enzymes or hepatitis. Similarly, cerebral thromboembolism and cerebral vasculitis would be unexpected (by virtue of greater specificity) if the IB listed only cerebral vascular accidents. "Unexpected," as used in this definition, also refers to AEs that are

mentioned in the IB as occurring with a class of drugs or as anticipated from the pharmacological properties of the drug but are not specifically mentioned as occurring with the particular drug under investigation.

16.7. Grading of Adverse Events

The severity (or intensity) of an AE refers to the extent to which it affects the subject's daily activities and will be classified by the investigator as mild, moderate or severe using the following criteria:

- Mild: Awareness of sign or symptom, but easily tolerated. Not likely to require medical attention.
- Moderate: Discomfort enough to cause some interference with daily activity. May require medical intervention.
- Severe: Intense enough to disrupt daily activities. Likely requires medical intervention.

16.7.1. Clarification of the difference in meaning between “severe” and “serious”

The term “severe” is often used to describe the intensity (severity) of a specific event (as in mild, moderate or severe myocardial infarction); the event itself, however, may be of relatively minor medical significance (such as severe headache). This is not the same as “serious”, which is based on the outcome or action criteria usually associated with events that pose a threat to life or functioning. Seriousness (not severity) serves as a guide for defining regulatory reporting obligations.

16.8. Causality Assessment

The investigator will assess causality (i.e., whether there is a reasonable possibility that the study drug caused the event) for all AEs and SAEs. The relationship will be characterized using the following classification:

- Related: The temporal relationship of the AE with the study drug makes causality possible and as likely or more likely than due to another cause such as other drugs, a surgical intervention, or an underlying disease.
- Not related: The temporal relationship of the AE with the study drug makes causality improbable and can be due to another cause such as other drugs, a surgical intervention, or an underlying disease.

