16.9. Adverse Event Collection Timeframe

AEs will be recorded and reviewed at all scheduled and unscheduled study visits from the time the ICF is signed through TOC visit. New AEs starting after TOC will be recorded only if they led to the use of other antifungal medications or topical vaginal treatment, if they are a vaginal bacterial or parasitic infection, or if they are deemed related to the previously administered study drug.

All AEs reported by the subject or observed by members of the clinical staff will be evaluated by the principal investigator (PI) or qualified designee. The PI will attempt, if possible, to establish a

diagnosis based on presenting signs and symptoms. The nature of the AE, time of onset relative to study drug administration, duration, severity, and relationship to treatment should be determined. Details of any corrective treatment must be recorded in the eCRF. The PI will determine whether any changes have occurred in baseline signs and symptoms. All AEs and SAEs will be collected in the eCRF.

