16.10. Serious Adverse Event Reporting Requirements

All SAEs must be reported within 24 hours of the site becoming aware of the SAE ([Appendix 3](#)). Any event that is serious, study drug-related, and unexpected as assessed by the medical monitor or the Sponsor will be submitted to the regulatory authorities in accordance with national regulatory laws and regulations. The PI will be responsible for reporting all SAEs that require reporting to the local or central Institutional Review Board/Ethics Committee (IRB/EC) in accordance with its regulations and guidelines.

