APPENDIX 3. SERIOUS ADVERSE EVENT REPORTING

SAEs, as defined in Section 16 Safety Assessments and Monitoring will be reported in accordance with ICH E2A Clinical Safety Data Management: Definitions and Standards for Expedited Reporting.

Site Responsibilities

All SAEs that occur during the course of the study must be reported to SCYNEXIS within 24 hours of the knowledge of the occurrence.

The Investigator will fill out the SAE form and provide as complete information as are available. At a minimum, subject number, the dates and times of the study drug administered, a narrative description of the event must be provided. An assessment by the Investigator as to the severity of the event and relatedness to study drug should also be provided, if possible. Investigator will report all SAEs to:

SCYNEXIS Inc.
[name]
[name]
[contact]
and

[contact] [contact] [contact]

The investigator will report SAE and any follow up information to the Research Ethics Board (REB) per REB procedures and requirements.

The investigator will provide SAE follow-up information as soon as information is available to SCYNEXIS.

SCYNEXIS Responsibilities

If the SAE is considered a Suspected, Unexpected Serious Adverse Reaction (SUSAR) SCYNEXIS or designee will create a CIOMS or a Medwatch 3500A Report for submission to the relevant regulatory authority within 15-days after SCYNEXIS has learned of the SAE. If the SUSAR is a fatal or life-threatening event, the reports will be sent within 7 days after SCYNEXIS has learned of the event.

Follow-up reports will be provided to regulatory agencies as soon as information is available according to the same reporting periods.

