6.6. Safety Analyses

6.6.1. Adverse Events

A Treatment-emergent adverse event (TEAE) is defined as any AE that occurs on or after the start time of the study drug administration. AEs will be coded using the MedDRA 26.0 dictionary.

A summary of TEAEs will be presented as the number and percentage of subjects with at least one of the following:

- Any AE
- Any TEAE

- Treatment-related TEAE
- Serious TEAE
- Treatment-related serious TEAE
- TEAE leading to study drug withdrawal
- TEAE leading to death

TEAEs will be summarized by SOC and preferred term for each treatment group. For subjects with the same SOC and preferred term occurring more than once, the first occurrence will be tabulated. TEAEs will also be presented for each preferred term by maximum severity, by highest relationship to study drug, and for serious AEs. In the overall summary, additionally, the number and percentage of patients with at least one severe TEAE, with at least one moderate TEAE but no severe TEAE and with only mild TEAEs will be provided.

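### Protocol 16.8 asks for a reasonable-possibility judgement of causality, but its two categories use different thresholds and leave a reasonable but lesser possibility without a clear label

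*Protocol*

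**What the plan says.** Protocol 16.8 requires a causality assessment for every AE and SAE and states the question as "whether there is a reasonable possibility that the study drug caused the event". It offers two categories:

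- Related, where the timing "makes causality possible and as likely or more likely than due to another cause such as other drugs", a surgical procedure or underlying disease.
- Not related, where the timing "makes causality improbable and can be due to another cause such as other drugs, a surgical intervention, or an underlying disease".

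The label is used in these places:

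- Protocol 14.19, 16.9 and Table 1 footnote j: AEs are recorded from consent through TOC whatever their relationship. After TOC a new AE is recorded by one of three routes: it led to other antifungal or topical vaginal treatment, it is a vaginal bacterial or parasitic infection, or "if they are deemed related to the previously administered study drug".
- SAP 6.6.1: counts of treatment-related TEAEs and treatment-related serious TEAEs, and tables "by highest relationship to study drug". The SAP does not redefine the categories.
- Protocol 16.10: submission to authorities applies to events that are "serious, study drug-related, and unexpected as assessed by the medical monitor or the Sponsor".

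Appendix 3, on the content of the SAE report, adds: "An assessment by the Investigator as to the severity of the event and relatedness to study drug should also be provided, if possible".

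**The concern.** The question put to the investigator and the answers on offer use different thresholds. A reasonable possibility is an absolute test: could the drug plausibly have caused this? Related is a comparative test: is the drug at least as likely as the alternative? Not related is a third standard again, improbability. An investigator who thinks the drug may well have contributed, but that another drug or a disease is the likelier cause, has no category that fits. Two investigators with the same view of the same event can therefore record opposite labels, each with support in the text.

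At stake are the consistency of the related-event tables and, after TOC, whether some events enter the database at all. Safety and tolerability is a secondary objective of the study (Protocol 8.2), so these outputs matter even though they are descriptive.

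**Working it through.** Section 16.8 states no figure, so there is nothing to recompute. The check sets the definitions side by side and then follows the label to where it is used.

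**Step 1. Three kinds of event against the three standards in 16.8.**

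| Investigator's view | Opening test | Related | Not related |
|---|---|---|---|
| Drug at least as likely as another cause | met | met | not met |
| Drug less likely than another cause, but a real possibility | met | not met | not met if improbable has its ordinary meaning; met if it only means less likely |
| Drug improbable, another cause available | not met | not met | met |

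The first and third rows are consistent. The middle row fails on either meaning of improbable. On the ordinary meaning the event has no category. On the weaker meaning it becomes Not related although it passes the section's own test.

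**Step 2. Is there a rule elsewhere that resolves the middle row?** Protocol 16.9, 16.10, 16.12 and Appendix 3, and SAP 6.6.1, contain no intermediate category, no default and no instruction for an unclassified relationship.

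**Step 3. Where does the label change what is recorded or tabulated?**

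- Through TOC: every AE is recorded, and TEAEs are tabulated by system organ class and preferred term. A middle-row event can be mislabelled but is not lost.
- After TOC, serious: Protocol 16.10, 16.12 and Appendix 3 require all SAEs to be reported, so these are not lost either.
- After TOC, non-serious, led to antifungal or topical vaginal treatment, or a vaginal infection: recorded whatever the label.
- After TOC, non-serious, all other events: recorded only if related. Here a middle-row event filed as Not related leaves no record. It is then missing from the all-causality TEAE tables too, and cannot be reclassified.

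**Step 4. How long does the post-TOC filter run in Cycle 1?** Take Baseline as Day 1, TOC at 14 days after Baseline, the last visit at 60 days after the end of treatment (EOT), and EOT as the last dosing day. TOC is then Day 1 + 14 = Day 15.

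- 1-day dosing: last visit Day 1 + 60 = Day 61; 61 − 15 = 46 days.
- 3-day dosing: Day 3 + 60 = Day 63; 63 − 15 = 48 days.
- 7-day dosing: Day 7 + 60 = Day 67; 67 − 15 = 52 days.

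The filter thus covers the larger part of Cycle 1, but dosing ends at least 8 nominal days before it begins (Day 15 against Day 7 at the latest). Subjects who enter Cycle 2 restart the schedule at Baseline. These are lengths of time, not counts of events.

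**The case against.** The strongest reply is that the opening sentence governs and the categories merely illustrate it, so that a sensible investigator would file a middle-row event as Related. That is possible, and it means the direction of any error is not fixed by the text. It does not remove the defect, because the explicit definition of Related excludes the event.

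A second reply is that the exposed set is small. All-causality tables remain, safety is descriptive, and the post-TOC period starts after Cycle 1 dosing has ended. Protocol 10.1.1.7 and 18.7.1 also speak of AE recording at all visits without repeating the post-TOC limit. This stands as a limit on size. The specific rule in 14.19, 16.9 and footnote j is nevertheless explicit, and it uses the label.

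A reader might infer more than the documents support:

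- *That expedited reporting is suppressed.* Sites report all SAEs whatever their causality, and relatedness for submission is assessed by the medical monitor or the sponsor (16.10, 16.12). The investigator's label is not the sole gate.
- *That post-TOC medication records depend on the label.* In 13.1 and 14.18 only a residual class of medications for AEs does. Antifungals, vaginal medications and antibiotics are recorded regardless, and Table 1 footnote i and section 18.7.1 do not restrict the residual class to related AEs.
- *That the bias is concentrated in Group B.* A subject can enter Group B on recurrent VVC or *Candida* species alone. Nothing shows how many have a competing disease or drug.
- *That the gap can be sized on a probability scale.* The documents give no probabilities, and being as likely as another cause does not imply 50% when there are several alternatives. The width of a gap on such a scale is not a share of events.
- *That Appendix 3 waives causality for SAEs.* Its qualifier follows a list of minimum content for a report due within 24 hours, with follow-up required, and can be read as covering the initial report only.

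**Conclusion.** The point holds as an internal contradiction in Protocol 16.8. The lead-in and the two categories do not describe the same test, and no other section resolves the difference. It is worth correcting because the label is a recording rule as well as a descriptor.

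The reach is limited to (a) new non-serious AEs after TOC outside the two label-independent routes, and (b) the treatment-related and highest-relationship tables in SAP 6.6.1. The number of events affected cannot be estimated from the documents, and whether related events would be under-counted depends on how investigators resolve the conflict. The primary endpoint is not affected.

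This rests on one assumption: that the eCRF, which is not among the documents, carries the same two categories without further guidance.

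**What to change.** Rewrite the two categories in 16.8 on the section's own test and as complements. Related means that a reasonable possibility of causation by the study drug exists; Not related means that no such possibility exists. Remove the comparison with other causes from the definition of Related and the improbability standard from Not related. Carry the same words into the eCRF text. The post-TOC recording rule and the SAP tables then need no change, since both take the label as given.

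At most, align Appendix 3 with 16.8 by stating that relatedness must be supplied at follow-up if it is absent from the initial SAE report.

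The cost is a wording amendment and an eCRF text update, with no new visit or procedure. The treatment-related rate may rise slightly and be less directly comparable with earlier studies if those used the present wording. If events have already been assessed under the present wording, the report should state that definition beside the related-event tables.

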16.9. Adverse Event Collection Timeframe

AEs will be recorded and reviewed at all scheduled and unscheduled study visits from the time the ICF is signed through TOC visit. New AEs starting after TOC will be recorded only if they led to the use of other antifungal medications or topical vaginal treatment, if they are a vaginal bacterial or parasitic infection, or if they are deemed related to the previously administered study drug.

All AEs reported by the subject or observed by members of the clinical staff will be evaluated by the principal investigator (PI) or qualified designee. The PI will attempt, if possible, to establish a

diagnosis based on presenting signs and symptoms. The nature of the AE, time of onset relative to study drug administration, duration, severity, and relationship to treatment should be determined. Details of any corrective treatment must be recorded in the eCRF. The PI will determine whether any changes have occurred in baseline signs and symptoms. All AEs and SAEs will be collected in the eCRF.

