Treatment Cycle 2: A second treatment cycle will be allowed for subjects who did not achieve sufficient clinical improvement (e.g. VSS remains ≥ 3) on the randomized treatment (Cycle 1) as evaluated at the TOC visit or at the FU EOT+14 visits. A second treatment cycle will also be allowed for subjects with clinical cure/improvement/success who experience a recurrence before the last FU visit. During Cycle 2, subjects may receive additional treatment with ibrexafungerp for a period up to 14 days as recommended by the investigator and following discussion with the sponsor.

It is recommended that study drug be administered with or immediately after a meal or snack.

STUDY BLINDING, RANDOMIZATION, AND STRATIFICATION: This is an open-label study. Subjects will be randomized to treatment, stratified by group based on the *Candida* species and presence or absence of underlying medical conditions.

STUDY EVALUATIONS

Efficacy Evaluations

Clinical Evaluation: The signs (edema, erythema, and excoriation or fissures) and symptoms (itching, burning, and irritation) of infection will be assessed by the investigator and the subject, respectively, on the VSS Scale. The VSS Scale is a standardized, predefined scale where each sign and symptom will be given a numerical rating based on severity (absent = 0; mild = 1; moderate = 2; or severe = 3) to calculate a total composite score.

Mycological Evaluations: Mycological tests will include direct WET Mount microscopic examination (performed locally) to visualize clue cells indicative of bacterial vaginosis or trichomonas, direct microscopic examination with 10% KOH (performed locally) to identify yeast, and fungal cultures (performed at the central lab) for species identification and antifungal susceptibility testing.

Safety and Tolerability Assessments

Safety Evaluations: Safety will be evaluated throughout the study, from consent through the TOC visit, including the following parameters: AEs, concomitant medications, vital signs, safety laboratory tests, and study treatment discontinuations.

STATISTICAL ANALYSES:

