16.12. Serious Adverse Event Reporting – Procedures for Investigators

Initial Reports and Follow-Up SAE Reports: To report an SAE, the SAE eCRF form within the Electronic Data Capture (EDC) system must be completed. All SAEs, whether or not deemed drug-related or expected, must be reported by the investigator or qualified designee within 24 hours of first becoming aware of the event ([Appendix 3](#)). The investigator/qualified designee will enter the required information regarding the SAE into the appropriate form, which will automatically result in distribution of the information to the appropriate sponsor contact. If the EDC system is temporarily unavailable (>24 hours), the event, including the investigator-determined causality to study drug, should be reported via a paper back-up SAE form to the Safety Surveillance team via (contact information, i.e., e-mail or fax will be available on the SAE form).

Upon return of the availability of EDC system, the SAE information must be entered into the EDC system as soon as possible. The SAE form within the EDC system must be updated within 24 hours of knowledge/receipt of SAE follow-up information.

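### The post-TOC limit on AE recording (16.9, 14.19, Table 1 footnote j) makes no exception for serious events and contradicts the SAE rules in 16.10, 16.12 and Appendix 3

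*Protocol*

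**What the plan says.** **AE recording rule.** Protocol 16.9 sets the collection timeframe. All AEs are recorded from consent to TOC. After that, "New AEs starting after TOC will be recorded only if they led to the use of other antifungal medications or topical vaginal treatment". The other two admitted categories are bacterial or parasitic vaginal infections, and events that qualify "if they are deemed related to the previously administered study drug". Sections 14.19 and Table 1 footnote j give the same three categories. None of the three places mentions seriousness.

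**Definition.** Section 16.2: "A SAE is defined as an AE meeting one of the following outcomes". A limit on which AEs are recorded therefore reaches SAEs on its face.

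**SAE reporting rules.** Section 16.10: "All SAEs must be reported within 24 hours of the site becoming aware of the SAE". Section 16.12: "All SAEs, whether or not deemed drug-related or expected, must be reported by the investigator or qualified designee within 24 hours", using the SAE form in the EDC system. Appendix 3: "All SAEs that occur during the course of the study must be reported to SCYNEXIS within 24 hours".

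**Other statements of the window.** The synopsis (Safety Evaluations) says "Safety will be evaluated throughout the study, from consent through the TOC visit". The synopsis Safety Analysis paragraph and 18.7.1 give no TOC cut-off, and 10.1.1.7 has AEs documented at every visit. Section 16.9 itself ends with "All AEs and SAEs will be collected in the eCRF".

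**SAP 6.6.1.** A TEAE is any AE from the start of dosing onward, with no end date. Serious TEAEs and TEAEs leading to death are tabulated. The SAP does not say how post-TOC events are counted or whether they come from the AE page or the SAE form.

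**The concern.** Take an unrelated hospitalisation on Day 40. Under 16.9 it fits none of the three categories and is not recorded. Under 16.12 and Appendix 3 it must reach the sponsor within 24 hours. A site can point to protocol text for either course, and the text that supports omission is the section on collection timeframe, repeated in the visit schedule that sites work from.

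Two things are at stake. First, 16.10 gives the medical monitor or sponsor the judgement of whether a serious event is related and unexpected. At a site that treats 16.9 as governing, the investigator's own relatedness call comes first and can keep the event from that review. Second, the SAP's serious-TEAE counts have no end of window, so they would depend partly on how each site read the protocol. Group B, which includes subjects with diabetes, immunocompromise or immunosuppressive therapy, is two thirds of planned enrolment.

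**Working it through.** The plan gives no figure to reproduce on this point. The check is a comparison of text, followed by arithmetic on the size of the affected window and the weight of one event.

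**1. Same event, each rule**

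| Source | Unrelated SAE starting after TOC |
|---|---|
| 16.9 (post-TOC list), 14.19, Table 1 footnote j | Not recorded |
| Synopsis, Safety Evaluations | Outside the stated window |
| 16.10, 16.12, Appendix 3 | Reported within 24 hours |
| 10.1.1.7, 18.7.1 | Recorded; no cut-off |
| 16.9, closing sentence | Recorded, but so is every other AE |

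The closing sentence of 16.9 cannot serve as an SAE exception. It covers all AEs equally, so reading it that way would cancel the restriction set earlier in the same section. No passage states an order of precedence.

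**2. Share of Cycle 1 follow-up under the restriction**

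Inputs (Protocol 10.1.1 and 12.1): TOC is 14 ± 3 days after Baseline, the last FU is 60 ± 4 days after EOT, and dosing lasts 1, 3 or 7 days. Counting days from Baseline, EOT falls on day 0, 2 or 6.

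Share = (EOT + 60 − 14) / (EOT + 60)

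- 1-day: (60 − 14)/60 = 46/60 = 76.7%
- 3-day: (62 − 14)/62 = 48/62 = 77.4%
- 7-day: (66 − 14)/66 = 52/66 = 78.8%

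Across visit windows, the lowest share is 1-day dosing with a late TOC and an early last FU: (56 − 17)/56 = 69.6%. The highest is 7-day dosing with an early TOC and a late last FU: (70 − 11)/70 = 84.3%.

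**3. Expected number of SAE subjects**

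Inputs (Protocol 7.1.4, ibrexafungerp arms only, since this trial has no placebo): 1 of 247 and 1 of 298 subjects.

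- 1/247 = 0.40%; × 150 = 0.6 subjects
- 1/298 = 0.34%; × 150 = 0.5 subjects
- Combined 2/545 = 0.37%; × 150 = 0.55 subjects; chance of at least one = 1 − (1 − 2/545)^150 = 42%

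These are whole-study rates in a different population, and the protocol gives no SAE timing for those studies. They indicate how rare SAEs are. They do not estimate how many would fall after TOC.

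**4. Weight of one event (exact 95% limits)**

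| | Counted | Not counted |
|---|---|---|
| Arm of 50 | 1/50 = 2.0% (0.05% to 10.65%) | 0/50 (upper limit 7.11%) |
| All 150 | 1/150 = 0.67% (0.02% to 3.66%) | 0/150 (upper limit 2.43%) |

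**5. Group B share:** (50 + 50)/150 = two thirds.

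**6. Cycle 2.** Entry follows the Cycle 1 TOC or a later visit, and the schedule then restarts at Baseline (Protocol 12.1 and 15). If the TOC limit does not reset, all of Cycle 2 dosing falls inside the restricted period. The documents do not say whether it resets.

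**The case against.** The strongest reply is that a specific SAE duty is not cut back by a general AE window. Three provisions are unconditional, 16.12 expressly sets causality aside, and a report made under it goes through the SAE form in EDC and so is already in the study's data system. Footnote j qualifies the AE monitoring row, and Table 1 has no SAE-reporting row. Many sites would read it that way, and this part of the reply stands.

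A reader might therefore be tempted to infer that every unrelated post-TOC SAE is dropped, or that the sponsor can never review one. The documents do not support that. It would be true only at a site that let 16.9 override 16.10, 16.12 and Appendix 3 together, and how sites will behave is conjecture. The synopsis is also less one-sided than its Safety Evaluations sentence suggests, because its Safety Analysis paragraph has no TOC limit.

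The stakes are also modest. The study is exploratory, no formal analysis of safety data is planned, the drug is already approved for VVC, and limiting non-serious AE recording after a short course is a defensible choice. Group B is not uniformly medically high-risk either, since recurrent VVC or certain isolates alone qualify a subject for it.

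None of this supplies a precedence rule or removes the word-for-word conflict. Nor does it tell the SAP programmer whether an SAE found only on the SAE form belongs in the serious-TEAE table.

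**Conclusion.** The contradiction is in the current text. Three places restrict post-TOC recording with no exception for serious events, one synopsis sentence ends safety evaluation at TOC, and three other places require all SAEs to be reported whatever their cause.

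The likely effect is inconsistent recording: the SAE form completed but not the AE page, and possible omission at a site that follows 16.9. Certain loss is not shown. The exposure is long, at 77-79% of nominal Cycle 1 follow-up, but few events are expected. With about 0.5-0.6 SAE subjects per 150, the issue will most likely concern no event or one, and that one would decide whether an arm shows 0% or 2%.

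This rests on nominal visit days, Cycle 1 only, planned enrolment of 150, and SAE rates carried over from the cited acute-VVC studies. The contradiction itself depends on none of these. It should be corrected because the omission concerns serious events and the correction costs almost nothing.

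**What to change.** - **Protocol 16.9, 14.19 and Table 1 footnote j:** state that the post-TOC restriction applies to non-serious AEs only, and that SAEs are recorded regardless of relationship to study drug through the last FU visit of the last cycle. This brings the AE sections into line with what 16.12 and Appendix 3 already require.
- **Synopsis, Safety Evaluations:** align the sentence that ends at TOC with the same window.
- **16.9, closing sentence:** reword it so that it no longer contradicts the restriction above it.
- **SAP 6.6.1:** give the end of the TEAE and SAE counting window, say whether SAE-form and AE-page records are reconciled before tabulation, and state how the post-TOC limit applies once a subject enters Cycle 2.

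The cost is one clause in three places, two reworded sentences and a short SAP paragraph. No visit is added, because AE monitoring is already marked at every FU visit in Table 1. The downside is possibly a few more SAE records.
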